Second, the project aims to evaluate the histological composition of an incisional tissue biopsy at 6 weeks post-operative healing in patients who undergo these procedures with

Version 2 - PROTOCOL # 0145-23-FB Page 6 of 27

Institutional Review Board (IRB)

either Mucograft Seal or Colla-Plug, which will provide valuable information on the tissue response to these biomaterials at an early stage of the healing process. By addressing these information gaps, the project aims to contribute to the development of more effective socket preservation techniques and biomaterials, which will benefit patients undergoing these procedures.

CHARACTERISTICS OF THE SUBJECT POPULATION

4. Accrual

A. Is this study conducted solely at sites under the oversight of the UNMC IRB (e.g. UNMC, Nebraska Medicine, CHMC, UNO)?

Yes

1. How many subjects will need to be consented (per group, as applicable) in order to achieve the scientific objectives of the research?

24 subjects will be enrolled - 12 in each group to account for a 10% drop out rate.

2. What is the statistical or other justification for the total number of subjects described above?

A sample size of 11 in each group provides 80% power to be able to detect an absolute difference in 20 percentage-points of converted mucosa between the collagen (i.e. 50%) and mucograft (i.e. 70%) groups at four weeks, assuming a standard deviation of 15 for percentage converted mucosa and an alpha level of 0.05, using a Wilcoxon Rank Sum test.

3. How long do you estimate it will take to accrue the required number of subjects?

9 months

5. Gender of the Subjects

A. Are there any enrollment restrictions based on gender?

No

6. Age Range of Subjects

A. Will adults be enrolled ?

Yes

1. What is the age range of the adult subjects?

19-75

2. What is the rationale for selecting this age range?

Version 2 - PROTOCOL # 0145-23-FB Page 7 of 27

Institutional Review Board (IRB)

IRB PROTOCOL # 0145-23-FB Page 8 of 27

This treatment is rarely performed in children below the age of 19 and after the age of 75, adult subjects will typically show decreased wound healing due to age which could conflate findings.

B. Will children (18 years of age or younger) be included in this research?

No

1. What is the justification for excluding children from participating in this research?

♦ Research is irrelevant to children (e.g. disease or condition rarely encountered in children).

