An additional post operative visit will occur at 6 weeks to do a final soft tissue healing evaluation. At this time a small (2mm) incisional biopsy will be taken and stored in 10% formalin that is labeled similarly to GCF sample tubes. We do not anticipate this tissue removal to have an impact on final healing of the underlying bone for the patient. This tissue will be processed with a hematoxylin and eosin stain and the width of keratinized tissue will be measured by a separate individual who is blinded to the treatment groups. GCF collection on the remaining adjacent teeth will also occur at this visit, as will an intraoral digital scan of the extraction site.

The final postoperative visit will be 3 months following the extraction. A limited-field CBCT will be taken to begin the process of implant treatment planning and measure bone height, width and volume. A final GCF collection on the remaining adjacent teeth will also occur at this visit, as will a final intraoral digital scan of the extraction

Version 2 - PROTOCOL # 0145-23-FB Page 11 of 27

Institutional Review Board (IRB)

IRB PROTOCOL # 0145-23-FB Page 12 of 27

site.

GCF Cytokine Determination

At the time of analysis, each pooled GCF samples will be eluted using 100 μ l of 1 \times PBS by gently agitating the samples on a rocker plate for 1 h at 4°C. Cytokine concentrations will be measured using a customized human cytokine and magnetic bead panel (Milliplex MAP kit; Millipore, Billerica, MA), and a MAGPIX instrument and software (Luminex Corporation, Austin, TX) per the manufacturers recommendations.

Ten analytes will be measured: interleukin-1 β (IL-1 β), IL-4, IL-6, IL-8, IL-10, IL-13, IL-17 granulocyte-macrophage colony-stimulating factor (GM-CSF), tumor necrosis factor alpha (TNF- α), interferon-gamma (INF- γ). Albumin for each sample also will be measured to normalize cytokine levels and control for serum contamination. The amounts of cytokines will be reported in picograms per albumin level and per 30-s sample.

Statistical Analysis

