The percentage of converted mucosa will be documented at six weeks after an extraction, and differences in the width of keratinized tissue between the collagen and mucograft groups will be assessed using a Wilcoxon Rank Sum test. As a secondary analysis, we may also look at other related demographic (e.g. sex, age, etc.) and clinical (e.g. bone width, soft tissue volume, cytokine levels, etc.) characteristics to see if they have associations with the percent keratinized gingiva, using Spearman correlations for continuous variables, or Wilcoxon Rank Sum/Kruskal Wallis tests for categorical variables.

C. Select any of the following that apply to the research:

Phase I study

♦ Randomization

Placebo (or non-treatment arm)

Washout

Sensitive surveys or questionnaires

None of the above

Option chosen: Randomization

Describe randomization process and schedule

A statistician will generate a randomization schedule, after which someone not involved in the treatment of these patients will put each randomized treatment assignment into separate

envelopes, which will be given to the clinical provider close to the time the material will be placed, after the patient has been enrolled/consented into the study.

Version 2 - PROTOCOL # 0145-23-FB Page 12 of 27

Institutional Review Board (IRB)

IRB PROTOCOL # 0145-23-FB Page 13 of 27

D. Identify:

1. All procedures, interventions, evaluations and tests performed solely for research purposes (eg, administration of an investigational drug or a new psychological assessment instrument; randomization)

Procedures performed solely for research purposes include: the collection of gingival crevicular fluid (GCF); soft tissue biopsy at 6-weeks post-procedure.

2. All procedures, interventions, evaluations and tests performed for clinical indication but more frequently than they would be if the subject was not participating in the research (eg, extra blood tests; additional radiology exams)

It is not typical to have an intraoral scan done at post-operative visits. However, this takes less than 2 minutes to perform and has no contraindications or risks. It is simply a data collection process for dentists to measure changes in our patients over time.

E. Describe briefly the statistical methods used to analyze the data (or reference the appropriate section of the detailed protocol or grant).

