Subject identifiers will be stripped from the data and destroyed once it is no longer required.

C. Will research data that contain subject identifiers be disclosed to:

Other investigators at UNMC, NM, UNO or CHMC who are not listed in Section I of this application?

No

2. Investigators outside of UNMC, NM, UNO or CHMC?

No

3. Will research data that contain subject identifiers be disclosed to any commercial sponsor or contract research organization (CRO), or to any other external organization or entity (e.g., NCI cooperative groups)?

No

D. What provisions will be in place to protect the subject's privacy? Check all that apply.

- ◆ Ensuring that only personnel listed on the IRB application Section I.3(A-E) are present during the consent process.
- ◆ Ensuring that the fewest number of individuals possible are aware of the subject's participation in the research.
- ◆ Ensuring that the research activities are performed in as private of a place as possible.

Other. Explain.

E. Does this research involve data banking at UNMC, NM, UNO or CHMC, or by an outside organization (e.g. NCI Cooperative Group, pharmaceutical company) for future research that is not related to this study?

No

RISK/BENEFIT ASSESSMENT

16. Potential Risks

What are the potential risks associated with each research procedure, intervention, evaluation and/or test? If data are available, estimate the probability that a given harm may occur and its potential reversibility.

Potential risks associated with soft tissue sampling at 4-weeks includes minimal pain and adjacent tooth sensitivity.

The soft tissue and GCF specimens will be collected in plastic-capped vials and frozen until

analysis. These vials will be labeled with the subject's number and visit (N1-0, N2-2) and will

not be labeled with any personal identifying information, thus breach of confidentiality is not

at risk.

Potential risks associated with limited view CBCT include increase exposure to radiation.

This risk is inherent to any dental radiography and the limited-view CBCT pre-extraction and post-extraction is standard therapy for dental implant treatment planning.

17. Risk Classification

What is the overall risk classification of the research?

Minimal risk

♦ Greater than minimal risk

18. Minimization of Risk

A. Describe how the subjects of the research will be monitored by the investigators and other research personnel to ensure their safety.

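### The trial is powered for percentage of converted mucosa at four weeks, but the only stated treatment-group test is on width of keratinized tissue at six weeks

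*Protocol*

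**What the plan says.** Section 4.A.2 names the target of the sample size as follows: "absolute difference in 20 percentage-points of converted mucosa between the collagen (i.e. 50%) and mucograft (i.e. 70%) groups at four weeks". For the variability and the method, that section then adds this: "assuming a standard deviation of 15 for percentage converted mucosa and an alpha level of 0.05, using a Wilcoxon Rank Sum test". The result is 11 per group for 80% power, raised to 12 per group for dropout.

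The statistical analysis text in 12.B, repeated word for word in 12.E, says: "The percentage of converted mucosa will be documented at six weeks after an extraction". The same sentence continues: "differences in the width of keratinized tissue between the collagen and mucograft groups will be assessed using a Wilcoxon Rank Sum test". The secondary analysis then relates other characteristics to the outcome "to see if they have associations with the percent keratinized gingiva, using Spearman correlations for continuous variables".

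The research plan in 12.B places the biopsy at six weeks ("An additional post operative visit will occur at 6 weeks to do a final soft tissue healing evaluation") and describes one reading of the specimen: "the width of keratinized tissue will be measured by a separate individual who is blinded to the treatment groups". Section 16, on risks, still has the earlier time: "Potential risks associated with soft tissue sampling at 4-weeks includes minimal pain and adjacent tooth sensitivity".

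**The concern.** The sample size and the analysis disagree on two things that fix what the trial tests: the variable and the time. The variable with power behind it has no stated comparison between treatments. The variable that is compared has no target difference, SD or power. The planning values are attached to four weeks, when no tissue is taken.

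If width and percentage are different quantities, a non-significant width result could not be read against the planned 20-point difference. There would also be two candidate histological outcomes, and either could be put forward as the main one after the results are known. An analysis plan that followed the protocol could not satisfy both sections.

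**Working it through.** **1. Side by side.**

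| | Sample size (4.A.2) | Analysis (12.B, 12.E) | Biopsy text (12.B) |
|---|---|---|---|
| Variable | percentage of converted mucosa | percentage recorded only; width tested; a third term, percent keratinized gingiva, in the secondary analysis | width only |
| Time | four weeks | six weeks | six weeks |
| Test between treatments | Wilcoxon rank sum | Wilcoxon rank sum, on width | – |
| Difference and SD | 20 points, SD 15 | none for width | none |

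The follow-up visits are at two weeks, six weeks and three months. The Wilcoxon and Kruskal-Wallis tests in the secondary analysis are for demographic and clinical characteristics; treatment group is not named there. So the width test is the only stated comparison of the two materials.

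**2. Reproducing the plan's figure.** Inputs from 4.A.2: 11 per group, difference 20 points, SD 15, alpha 0.05. The section does not say whether the test is one- or two-sided; two-sided is assumed, with normal data.

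- Standardized difference: d = 20/15 = 1.333.
- Approximation: the two-sample t-test needs 9.89 per group for 80% power. Multiplying by π/3 for the Wilcoxon test under normality gives 9.89 × 1.047 = 10.36, rounded up to 11.
- Exact test by simulation: with 11 per group there are 11 × 11 = 121 pairs. The test rejects if U ≤ 30 or U ≥ 121 − 30 = 91, and its true size is 0.0473.

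| Patients per group | Power at d = 1.333 |
|---|---|
| 10 | 0.76 |
| 11 | 0.82 |
| 12 | 0.85 |

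Eleven is the smallest group size that reaches 80%. The calculation is correct for the percentage.

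**3. When that power carries over to width.** The Wilcoxon statistic depends only on ranks. Write percentage = 100 × W/L, with W the width and L the length it is divided by. If L is the same in every patient, ordering by W and ordering by percentage are identical, so U, the p-value and the power are identical. If L varies between patients, or if the percentage is not built from width at all, the two orderings can differ and the 0.82 no longer applies. The protocol gives no formula, no denominator and no statement that the two are the same.

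**4. What any tested variable would need.** Solving for 80% power at 11 per group gives d of about 1.30. For the percentage at six weeks this means:

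- at SD 15, a difference of at least 1.302 × 15 ≈ 19.5 points;
- at 20 points, an SD of at most 20/1.302 ≈ 15.4.

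For width there is nothing in the document to set against 1.30. Purely as illustration, with assumed standardized differences in width and 11 per group:

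| Assumed difference in width (SD) | Power |
|---|---|
| 0.5 | 0.19 |
| 0.8 | 0.40 |
| 1.0 | 0.57 |
| 1.2 | 0.73 |
| 1.333 | 0.82 |

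**The case against.** The strongest reply is that the three terms mean one histological measure. Both sections use the same test and the same two groups. The analysis text places percentage and width in one sentence and then treats a percentage as the outcome just analysed. The abstract's primary outcome is the histological composition of tissue at six weeks, and the biopsy text describes one specimen of stated size with one reading, from which a percentage could be derived. With a constant denominator the rank test is the same and only the wording is at fault. Four weeks also looks like leftover text, since every passage that schedules the biopsy says six. The power table for width rests on assumed values and is no evidence that power is actually lost.

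Much of this stands. The one-quantity reading is plausible, under it no power is lost, and the table shows only a range of what could happen. The timing of the biopsy itself is not in doubt. But the protocol never states that the terms are equivalent or that the denominator is constant. An analysis plan could define how the percentage is read, but it could not follow both sections as they stand. Even under the one-quantity reading, the 50%, 70% and SD 15 assumptions remain tied to a time at which nothing is measured.

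**Conclusion.** The concern holds and should be corrected before the histology is analysed. As written, the 80% power belongs to a variable and a time that the stated test does not use. The sample size arithmetic is not in error: power is about 0.82 for the percentage at 11 per group, assuming a two-sided exact test and normal data.

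The effect on the width test cannot be computed from the document. It is nil if width and percentage rank patients identically and unknown otherwise. The point is serious because this is the only treatment comparison for which the protocol states a test. That the sections conflict is certain; that power is lost is not.

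**What to change.** In 12.B and 12.E, apply the Wilcoxon comparison of the two groups to the percentage of converted mucosa at six weeks, and report width as supportive. This fits the sample size, the composition outcome in the abstract and the percentage used in the secondary analysis. Add the blinded reading of that percentage to the six-week biopsy text, and use the same term in the secondary analysis. In 4.A.2, replace four weeks by the six-week biopsy and confirm that 50%, 70% and SD 15 apply then. Align the time in section 16.

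Two alternatives would also resolve the conflict:

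- If width is the intended outcome, keep the test and restate 4.A.2 with a difference and SD for width. The 80% cannot simply be carried over.
- If the terms mean one quantity, say so, give the denominator, and use one name in 4.A.2, 12.B and 12.E. The time point still needs correcting.

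The main fix costs wording in four sections and at most one further reading on each of at most 24 existing slides, by the same blinded reader, with no extra visits or patients. The width alternative needs justified planning values and could change the sample size.

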Sponsored Programs Administration (SPA)/UNeHealth grants and contracts

Pathology approval for collection of tissue samples required for this study

Radiation Committee Approval

Other Review

♦ None of the above organizational requirements apply to this study

Institutional Review Board (IRB)

IRB PROTOCOL # 0145-23-FB Page 27 of 27

SECTION IV

COVID-19

Human Subjects Research Safety Plan

For studies involving face-to-face encounters, the research team under the responsibility of the principal investigator will agree to comply with the following safety measures:

1. Masking of the researcher(s) during a face-to-face encounter
2. Cleansing of any surface and/or equipment utilized before and after a subject encounter
3. The Biosafety Officer ([contact]) will be notified if obtaining saliva, nasal, sputum or stools samples to ensure safe collection, handling, and processing plan is in place
4. Suggest addressing the current health of the subject before commencing faceto-face research via questions below:

Have you or anyone in your household tested positive or had a fever, chills, cough, shortness of breath, diarrhea, nausea, vomiting, recent loss of taste or smell, tiredness or fatigue, or muscle aches? If yes, the monitor will not be allowed on campus.

Have you recently traveled to an area with a widespread outbreak or had close contact with a person known to have COVID-19, MERs-CoV or Ebola?

Have you traveled outside of the country within the past month? If so, where did you travel and when did you return?

Have you had a recent SARS-COV-2 antibody test or nasal swab and if so

when and what were the results?

♦ I acknowledge this requirement.

Powered by TCPDF (www.tcpdf.org)

Version 2 - PROTOCOL # 0145-23-FB Page 27 of 27 IRB PROTOCOL # 0145-23-FB Page 1 of 27


[name] - 2024-02-19 15:31:07.160 Version 2 - PROTOCOL # 0145-23-FB Page 4 of 27 Institutional Review Board (IRB) IRB PROTOCOL # 0145-23-FB Page 5 of 27 SECTION II PROTOCOL ABSTRACT 1. Provide a brief (less than 2500 characters) abstract of the research protocol. (2500 characters) This summary should include: 1) a brief description of the purpose of the study, 2) eligibility criteria, 3) interventions and evaluations and 4) follow-up. The purpose of this study is to compare the effectiveness of a porcine collagen membrane to a bovine collagen wound dressing for atraumatic extractions. These are both commonly used as a barrier and containment material over atraumatic extraction sites that

are grafted for future implant placement. The study will include nonsmoking adults aged 18-75 requiring premolar or anterior tooth extraction and graft procedures, who are in good general health and willing to provide informed consent. Exclusion criteria include a history of radiation therapy or bisphosphonate use, pregnancy or breastfeeding, systemic conditions that affect bone healing, contraindications to dental implants, and inability to attend follow-up visits. The study will be a double-blind randomized controlled trial involving 24 patients who will be assigned to two groups. Prior to tooth extraction, baseline data will be collected; including gingival crevicular fluid (GCF) sampling, and a limited field Cone Beam Computed Tomography (CBCT) radiograph. A reference digital scan will be taken to measure volumetric changes in soft tissue. Routine, atraumatic extraction of the tooth under local anesthetic will be performed. Following extraction, hydrated AllOss 50/50 DFDBA:DFDBA bone particulate will be condensed following a routine protocol. One group will receive Mucograft Seal over the graft, and the other group will receive Integra HeliPlug. Patients will be seen at a standard 2-week follow up to remove sutures, have a GCF sampling at the adjacent teeth and take another digital scan. Patients will be seen for an additional 6-week follow up to take a small (2mm) incisional biopsy for histological analysis. Another digital scan and GCF sampling will be taken. Final evaluation will be 3 months post-extraction and will include a localized CBCT evaluation for implant planning and another measure of soft tissue changes with a digital scan. At the time of implant surgery, the core of bone removed during osteotomy will be histologically analyzed for percentage of vital bone. Adverse events will also be recorded at each visit. The primary outcome measure will be the histological composition of tissue at 6 weeks and volumetric tissue changes. The secondary outcome measures will be adverse events, bone density on the post-operative CBCT and percentage of vital bone at implant placement.

PURPOSE OF THE STUDY AND BACKGROUND

2. Purpose of the Study

What are the specific scientific objectives of the research? The primary objectives of this study are to compare the efficacy of a porcine collagen Version 2 - PROTOCOL # 0145-23-FB Page 5 of 27 Institutional Review Board (IRB) IRB PROTOCOL # 0145-23-FB Page 6 of 27 membrane to a bovine collagen wound dressing for atraumatic extractions, in terms of their ability to act as a barrier and containment material over atraumatic extraction sites that are grafted for future implant placement. This will be measured by volumetric and linear dimensional changes in the soft tissue and the histological composition of keratinized tissue after healing.

The secondary objectives of the study are to evaluate the radiographic bone density and percentage vital bone at implant planning and placement.

3. Background and Rationale

Describe the background of the study. Include a critical evaluation of existing knowledge, and specifically identify the information gaps that the project is intended to fill.

Extraction and graft procedures are commonly performed in dental clinics where future implant placement is desired due to the large soft and hard tissue dimensional changes that occur as a socket heals (Araujo 2005, Chappuis 2017). While there are several techniques for ridge preservation, it is generally accepted that minimizing trauma from the extraction and

flap reflection greatly decreases loss of hard and soft tissue (Fickl 2008). This is why a popular method is some form of Bio-Col technique where a bone graft is condensed into the socket and then a collagen wound dressing, or plug, is used to prevent wash out of the graft. (Sclar 1999, Kotsakis 2014). While cost effective, and easy to place without flap reflection, a collagen plug can be dislodged quickly and has been shown to have a large soft tissue loss during healing (Morelli 2020, Thoma 2018). Therefore, other soft tissue alternatives have been investigated as an alternative membrane (Ghanaati 2017) Several studies have investigated the efficacy of Mucograft Seal as a barrier membrane to promote bone regeneration in socket preservation techniques. (Jung 2013) Mucograft Seal is a porcine collagen membrane that is shaped ideally for easy coverage of a socket. Because it is a pure matrix of Type I and Type III collagen, it is able to stay more dimensionally stable, making it an ideal material to combat soft tissue reduction as a site heals. It is currently used as a replacement for free gingival grafting coverage, such as with the soft tissue punch technique (Jung 2004), but has not been compared to a collagen wound dressing for critical early healing characteristics such as inflammatory cytokines. Additionally, there is limited information on the specific histological composition at 6 weeks post-operative healing in patients who undergo socket preservation with Mucograft Seal or Colla-Plug.

Information Gaps: The information gaps that this project is intended to fill are twofold. First, it aims to compare the effectiveness of Mucograft Seal and Colla-Plug in premolar and forward extraction and graft procedures through a randomized controlled trial, which will provide more conclusive evidence on the comparative efficacy of these two biomaterials. Second, the project aims to evaluate the histological composition of an incisional tissue biopsy at 6 weeks post-operative healing in patients who undergo these procedures with Version 2 - PROTOCOL # 0145-23-FB Page 6 of 27 Institutional Review Board (IRB) IRB PROTOCOL # 0145-23-FB Page 7 of 27 either Mucograft Seal or Colla-Plug, which will provide valuable information on the tissue response to these biomaterials at an early stage of the healing process. By addressing these information gaps, the project aims to contribute to the development of more effective socket preservation techniques and biomaterials, which will benefit patients undergoing these procedures.

CHARACTERISTICS OF THE SUBJECT POPULATION

4. Accrual A. Is this study conducted solely at sites under the oversight of the UNMC IRB (e.g. UNMC, Nebraska Medicine, CHMC, UNO)? Yes

1. How many subjects will need to be consented (per group, as applicable) in order to achieve the scientific objectives of the research? 24 subjects will be enrolled - 12 in each group to account for a 10% drop out rate.
2. What is the statistical or other justification for the total number of subjects described above? A sample size of 11 in each group provides 80% power to be able to detect an absolute difference in 20 percentage-points of converted mucosa between the collagen (i.e. 50%) and mucograft (i.e. 70%) groups at four weeks, assuming a standard deviation of 15 for percentage converted mucosa and an alpha level of 0.05, using a Wilcoxon Rank Sum test.
3. How long do you estimate it will take to accrue the required number of subjects? 9 months
5. Gender of the Subjects A. Are there any

enrollment restrictions based on gender? No 6. Age Range of Subjects A. Will adults be enrolled ? Yes 1. What is the age range of the adult subjects? 19-75 2. What is the rationale for selecting this age range? Version 2 - PROTOCOL # 0145-23-FB Page 7 of 27 Institutional Review Board (IRB) IRB PROTOCOL # 0145-23-FB Page 8 of 27 This treatment is rarely performed in children below the age of 19 and after the age of 75, adult subjects will typically show decreased wound healing due to age which could conflate findings. B. Will children (18 years of age or younger) be included in this research? No 1. What is the justification for excluding children from participating in this research? ♦ Research is irrelevant to children (e.g. disease or condition rarely encountered in children). Knowledge being sought in the research is already available for children or will be obtained from another ongoing study. A separate study in children is warranted and preferable. Insufficient data are available in adults to judge the potential risk in children. Other. Explain. 7. Race and Ethnicity Are there any subject enrollment restrictions based upon race or ethnic origin? No 8. Vulnerable Subjects A. Will prisoners be included in the research? No B. Select from the list all of the vulnerable populations that will specifically be recruited to participate in this research. Decisionally-impaired persons Critically ill patients Students of the investigator Employees of the investigator Educationally disadvantaged individuals Socially or economically disadvantaged individuals Individuals with a stigmatizing illness or condition Individuals from a marginalized social or ethnic group Other. ♦ No vulnerable subjects will be specifically recruited 9. Inclusion Criteria What are the specific inclusion criteria? Version 2 - PROTOCOL # 0145-23-FB Page 8 of 27 Institutional Review Board (IRB) IRB PROTOCOL # 0145-23-FB Page 9 of 27 1) adult patient seeking care at the UNMC College of Dentistry for extraction of a premolar or anterior tooth due to periodontal or endodontic defect, non-restorable caries or fracture 2) adult patient is considering dental implant placement to replace the extracted tooth and requires a bone grafting procedure in preparation for a dental implant 3) Nonsmoker 4) 19-75 years old 10. Exclusion Criteria What are the specific exclusion criteria? Exclusion criteria include a history of radiation therapy or bisphosphonate use, pregnancy, systemic conditions that affect bone and soft tissue healing, contraindications to dental implants, and inability to attend follow-up visits. 11. Pregnancy and Contraception Requirements A. Are women of child bearing potential (WOCBP) included in this research? Yes a. Are there any specific contraception requirements for subjects? No 1. Provide justification for absence of contraception requirements ♦ There are no interventions that are likely to be of risk to a fetus Investigational drug(s) is (are) not systemically absorbed Investigational drug(s) is (are) systemically absorbed, but there is no evidence from human studies, or from clinical experience, that there is risk to a fetus Other B. Are pregnant women included in this research? No 1. Provide justification for excluding pregnant women Investigational drug(s) is (are) absorbed systemically, and there is evidence from animal or human studies, or from clinical experience, that there is risk to a fetus OR investigational drug(s) is (are) absorbed

systemically, and there is a well-understood mechanism of action that may result in risk to a fetus Intervention includes a procedure expected to be of risk to a fetus (eg, exposure to ionizing radiation, maximal exercise test) Research is not relevant to pregnant women (e.g. disease or condition rarely encountered in pregnant women) Version 2 - PROTOCOL # 0145-23-FB Page 9 of 27 Institutional Review Board (IRB) IRB PROTOCOL # 0145-23-FB Page 10 of 27 Knowledge being sought in the research is already available for pregnant women or will be obtained from another ongoing study A separate study in pregnant women is warranted and preferable ♦ Physiology of pregnancy precludes generalization to other populations Other - explain 2. Describe how pregnancy status will be assessed (eg, self-report, urine pregnancy test, blood pregnancy test) and the frequency of monitoring during participation in the research. Pregnancy status will be determined via self-report 3. Describe the plan should a female subject, or the partner of a male subject, become pregnant while research interventions are on-going (or during the period that contraception is required following the completion of the intervention). Should a female subject become pregnant while research interventions are on-going, she will be dismissed from study. C. Are breast feeding women excluded in this research? No Provide justification for the inclusion or exclusion of breast feeding women. There are no interventions that are likely to be of risk to a nursing newborn. METHODS AND PROCEDURES 12. Methods and Procedures Applied to Human Subjects A. Are there any evaluations or tests that will be performed for the purpose of determining subject eligibility which would not be routinely conducted as part of standard clinical care of the prospective subject? No B. Describe the research plan, including all procedures, interventions, evaluations and tests. Patients at the UNMC College of Dentistry who are seeking care to extract a premolar or anterior tooth due to a periodontal defect, endodontic defect or non-restorable caries or fracture, and who are considering a dental implant to replace the extracted tooth, will be made aware of this clinical study by the dental faculty or residents planning the treatment. Subjects will be given the consent form to take home and consider, and any questions will be answered, signed and witnessed. Version 2 - PROTOCOL # 0145-23-FB Page 10 of 27 Institutional Review Board (IRB) IRB PROTOCOL # 0145-23-FB Page 11 of 27 Twenty-four patients will be enrolled in this study. On the day of extraction, baseline data will be recorded/collected. These include the following: 1. A limited field CBCT will be taken of the tooth to be extracted. 2. Gingival crevicular fluid (GCF) sampling at the interproximal sites of teeth adjacent to the tooth to be extracted. The tooth to be extracted will be isolated with cotton rolls and GCF collection paper strips will be placed into the facial and lingual interproximal gingival sulci for 30 seconds. The paper samples will be pooled and placed in a plastic-capped vial labeled with the subject number and visit (example: N1-0, N2-1) and immediately frozen at -80° C. The GCF sample vials will not be labeled with any personal identifying information (subject 's name, age, tooth #, etc). 3. A digital intraoral scan will be taken to establish baseline tissue dimensions. Routine atraumatic dental extraction under
